2.1 HYPOTHESIS

INO-4800 delivered ID followed immediately by EP will be well-tolerated, exhibit an acceptable safety profile, result in generation of cellular and humoral immune responses to SARS-CoV-2 Spike glycoprotein and provide protection against virologically-confirmed COVID-19 disease in subjects at high risk of SARS-CoV-2 exposure.

3.0 CLINICAL TRIAL DESIGN AND ENDPOINTS

This is an operationally seamless Phase 2/3, randomized, placebo-controlled, multicenter trial to evaluate the safety, immunogenicity, and efficacy of INO-4800, administered by ID injection followed immediately by EP using the CELLECTRA® 2000 device, in a 2-dose regimen (Days 0 and 28) in adults who are at high risk of SARS-CoV-2 exposure. Subjects 18 years of age and older are expected to be enrolled across two (2) segments of this study. In the Phase 2 segment, approximately 400 seronegative subjects will be enrolled. In the Phase 3 segment, approximately 6714 seronegative subjects are expected to be enrolled, and 402 seropositive subjects will be enrolled. The subjects and data from Phase 2 are independent from that of Phase 3. The primary objectives of this trial are to identify in seronegative subjects an optimal age-related dose (Phase 2 segment) for subsequent evaluation for efficacy (Phase 3 segment).

Phase 2 Segment – Dose Selection

INO-4800	COVID19-311
Inovio Pharmaceuticals, Inc.	Clinical Protocol

In the Phase 2 segment, approximately 400 subjects 18 years of age and older will be evaluated across four (4) dose groups (Table 1, Figure 1). Subjects will be randomized at a 3:3:1:1 ratio to receive either 1.0 mg or 2.0 mg of active investigational product (INO-4800) or 1 or 2 injections of placebo (SSC-0001). Dose groups receiving INO-4800 will enroll approximately 150 subjects per group. Dose groups receiving placebo will enroll approximately 50 subjects per group. Randomization will be such that approximately 240 subjects aged 18-50 years, 120 subjects aged 51-64 years and 40 subjects aged \geq 65 years will be enrolled. Initial enrollment will include subjects aged 18-50 years. Initiation of enrollment of older subjects 51-64 years of age and elderly subjects 65 years and older will depend on review of safety and immunogenicity data from those age groups generated in the Phase 1 study (COVID19-001).

Dose selection for evaluation of efficacy in the Phase 3 segment will be based on Week 6 immunogenicity data and Week 8 safety data from the Phase 2 segment. Group-level unblinded summaries and analyses of safety will be produced once the Week 8 phone call visit data are completed for all subjects in the Phase 2 segment. Group-level unblinded summaries and analyses of immunogenicity will be produced once the Week 6 visit data are completed for all subjects in the Phase 2 segment.

Phase 3 Segment – Efficacy

In the Phase 3 segment, approximately 6714 seronegative and 402 seropositive subjects 18 years of age and older will be randomized at a 2:1 ratio to receive either active investigational product (INO-4800, 1mg) or placebo (SSC-0001). Approximately half of seronegative subjects and approximately half of seropositive subjects will be 18-50 years of age, and the other half will be \geq 51 years of age. Also, a minimum of 10% of the total sample size will be \geq 65 years of age.

Subjects will be randomized in a stratified manner according to (a) age category (18-50 years vs. ≥51 years) on Day 0, and (b) presence of or absence on Day 0 of any of the following underlying medical conditions that increase risk of severe COVID-19 disease, per CDC criteria [1], as listed below:

- Cancer
- Chronic kidney disease
- Chronic lung diseases, including Chronic obstructive pulmonary disease (COPD), asthma (moderate-to-severe), interstitial lung disease, cystic fibrosis, pulmonary hypertension
- Neurologic conditions including stroke or cerebrovascular disease, that do not impact cognition
- Diabetes (type 1 or type 2)
- Hypertension
- Heart conditions, such as heart failure, coronary artery disease, or cardiomyopathies
- HIV infection (CD4 count >200 cells/mm3 or undetectable viral load)
- Liver disease
- Obesity (BMI \geq 30 kg/m2)
- Sickle cell disease or thalassemia, or
- Smoking (current or former smoker).

This segment of the trial is case-driven. Among seronegative subjects, a total of 149 observed cases will be required for 90% power to declare the vaccine efficacious (>30%), assuming a true efficacy of 60%. A sample size of 6714 seronegative subjects is expected to be required to achieve the 149 cases assuming an underlying attack rate of 3.7%. The

INO-4800	COVID19-311
Inovio Pharmaceuticals, Inc.	Clinical Protocol

actual sample size may differ if the observed attack rate is different than projected. There are two formal interim analyses of efficacy; one when 50% of the cases accrue and one when 75% of the cases accrue. If the prespecified criteria for efficacy are met at either interim analysis, then enrollment will continue until 4500 subjects have been enrolled, and blinded follow-up will continue until at least those 4500 subjects have a minimum of 6 months of safety follow-up. At that point, the trial would be unblinded and placeborecipients will be offered the active product.

The primary efficacy endpoint window will begin 14 days post-dose 2 and will end at 12 months post-dose 2. All Phase 3 segment subjects will be followed for 56 weeks from the Day 0 dosing [i.e., Week 56 will be the planned End of Study (EOS) visit for this segment of the trial].

External Committee Reviews

For both the Phase 2 and 3 segments, the Data Safety Monitoring Board (DSMB) will convene regularly to review all available unblinded safety data, and additionally upon completion of the Week 8 phone call visit for all subjects enrolled during the Phase 2 segment. For the Phase 3 segment, the DSMB will also review efficacy in an unblinded fashion. Additionally, for Phase 3, an independent, blinded Endpoint Adjudication Committee (EAC) will review and confirm COVID-19 cases.

Details of each committee's scope will be provided in the respective charters.

3.1 **PRIMARY OBJECTIVES**

See Table 6.

3.2 **PRIMARY ENDPOINTS**

Table 6: Primary Objectives and Associated Endpoints

Phase 2 Primary Objective	Phase 2 Primary Endpoints	
 Evaluate the cellular and humoral immune response to INO-4800 administered by ID injection followed immediately by EP 	 1a. Antigen-specific cellular immune response measured by IFN-gamma ELISpot assay 1b. Neutralizing antibody response measured by a pseudovirus-based neutralization assay 	
Phase 3 Primary Objective	Phase 3 Associated Primary Endpoint	
1. Evaluate the efficacy of INO-4800 in the prevention of COVID-19 disease in subjects who are SARS-CoV-2 negative at baseline	 Incidence of virologically-confirmed COVID-19 disease starting 14 days after completion of the 2-dose regimen until 12 months post-dose 2 (End of Study (EOS)) in subjects who are SARS- CoV-2 seronegative at baseline 	

3.3 SECONDARY OBJECTIVES

See Table 7.

3.4 SECONDARY ENDPOINTS

Table 7: Secondary Objectives and Associated Endpoints

Phase 2 Secondary Objectives | Phase 2 Secondary Endpoints

COVID19-311 Protocol | VV-TMF-00448 | 5.0

INO-4800	
Inovio Pharmaceuticals, Inc.	

COVID19-311 Clinical Protocol

1. Evaluate the safety and tolerability of INO-4800 administered by ID	1a. Incidence of solicited and unsolicited injection site reactions
injection followed immediately by EP	 Incidence of solicited and unsolicited systemic adverse events (AEs) by system organ class (SOC), preferred term (PT), severity and relationship to investigational product
	1c. Incidence of serious adverse events (SAEs)
	1d. Incidence of adverse events of special interest (AESIs)
Phase 3 Secondary Objectives	Phase 3 Secondary Endpoints
1. Evaluate the safety and tolerability of INO-4800	1a. Incidence of solicited and unsolicited injection site reactions
	 Incidence of solicited and unsolicited systemic adverse events (AEs) by system organ class (SOC), preferred term (PT), severity and relationship to investigational product
	1c. Incidence of serious adverse events (SAEs)
	1d. Incidence of adverse events of special interest (AESIs)
	1e. Incidence of all-cause mortality
2. Evaluate efficacy of INO-4800 in the prevention of COVID-19 disease according to degrees of disease severity in subjects who are SARS-	2a. Incidence of non-severe COVID-19 disease in SARS-CoV-2 seronegative subjects starting 14 days after completion of the 2-dose regimen until EOS
CoV-2 seronegative at baseline	2b. Incidence of severe COVID-19 disease in SARS- CoV-2 seronegative subjects starting 14 days after completion of the 2-dose regimen until EOS
	2c. Incidence of deaths due to COVID-19 in SARS- CoV-2 seronegative subjects starting 14 days after completion of the 2-dose regimen until EOS
3. Evaluate the cellular and humoral immune response to INO-4800	3a. Antigen-specific cellular immune response measured by IFN-gamma ELISpot
	3b. Neutralizing antibody response measured by a pseudovirus-based neutralization assay
4. Evaluate the efficacy of INO-4800 in the prevention of COVID-19 disease in subjects who are SARS- CoV-2 seropositive at baseline	 Incidence of virologically-confirmed COVID-19 disease starting 14 days after completion of the 2-dose regimen until 12 months post-dose 2 (End of Study (EOS)) in subjects who are SARS- CoV-2 seropositive at baseline

3.5 **EXPLORATORY OBJECTIVE**

See Table 8.

3.6 EXPLORATORY ENDPOINTS

Table 8: Exploratory Objectives and Associated Endpoints

Phase 2 Exploratory Objective	Objective Phase 2 Exploratory Endpoints	
1. Evaluate the expanded	1a. Antigen-specific cellular immune response	
immunological profile of antibody	measured by flow cytometry.	

INO-4800	
Inovio Pharmaceuticals, Inc	;.

		7	
	response and T cell immune response	1b. Expanded immunological profile which may include additional assessments of T and B cell numbers and molecular changes by measuring immunologic proteins and mRNA levels of genes of interest as determined by sample availability	
Pł	nase 3 Exploratory Objective	Phase 3 Exploratory Endpoints	
1.	Evaluate the efficacy of INO-4800 in the prevention of COVID-19 disease from SARS-CoV-2 variants in subjects who are SARS-CoV-2 seronegative at baseline	 Incidence of virologically-confirmed COVID-19 disease from a SARS-CoV-2 variant starting 14 days after completion of the 2-dose regimen until 12 months post-dose 2 (End of Study (EOS)) in subjects who are SARS-CoV-2 seronegative at baseline 	
2.	Evaluate the efficacy of INO-4800 in the prevention of SARS-CoV-2 asymptomatic infection in subjects who are SARS-CoV-2 seronegative at baseline	2. Incidence of SARS-CoV-2 asymptomatic infections in SARS-CoV-2 seronegative subjects starting 14 days after completion of the 2-dose regimen until EOS	
3.	Evaluate the immunological profile by assessing both antibody	3a. SARS-CoV-2 Spike glycoprotein antigen- specific binding antibody levels	
	response and T cell immune response	 Antigen-specific cellular immune response measured by flow cytometry 	
4.	Evaluate antibody persistence	4a. SARS-CoV-2 Spike glycoprotein antigen specific binding antibody levels at Week 30 or later.	
		4b. Neutralizing antibody response measured by a pseudovirus-based neutralization assay at Week 30 or later	

3.7 EFFICACY ASSESSMENT (PHASE 3 SEGMENT ONLY)

Subjects will receive either active investigational product (INO-4800, dose selected from the Phase 2 segment) or placebo (SSC-0001) in a 2-dose regimen administered intradermally followed immediately by EP on Days 0 and 28. Subjects will be monitored through regularly scheduled clinic visits and phone calls throughout the trial. Subjects will be regularly tested for SARS-CoV-2 infection using serologic testing. If COVID-19 disease is suspected based on symptoms or laboratory testing, site personnel will arrange for a clinic visit. Subjects with symptom(s) or a positive SARS-CoV-2 test result will be reviewed by the independent blinded EAC.

The mechanism for review and confirmation of cases will be outlined in an EAC Charter.

3.7.1 CASE DEFINITION FOR VIROLOGICALLY-CONFIRMED COVID-19 DISEASE:

- Positive testing by SARS-CoV-2 RT-PCR assay (performed at central lab*) with fever (temperature of 100.4°F/38.0°C or higher), or
- Positive testing by SARS-CoV-2 RT-PCR assay (performed at central lab*) with any of the following COVID-19 related symptoms:
 - Feeling feverish or chills
 - Cough
 - Shortness of breath or difficulty breathing
 - Fatigue
 - Muscle or body aches
 - Headache
 - New loss of taste or smell
 - Sore throat

INO-4800	COVID19-311
Inovio Pharmaceuticals, Inc.	Clinical Protocol

- Congestion or runny nose
- Nausea or vomiting
- Diarrhea

*Local lab results will be accepted if the subject is hospitalized and a sample is not able to be obtained for analysis at central lab.

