3.7.1.1 Case Definition for Severe COVID-19

- Confirmed COVID-19 disease (per Section 3.7.1) with any of the following:
 - a. Clinical signs at rest indicative of severe systemic illness (respiratory rate ≥ 30 per minute, heart rate ≥ 125 per minute, SpO2 ≤ 93% on room air at sea level or PaO2/FiO2 < 300 mm Hg),
 - b. Respiratory failure (defined as needing high-flow oxygen, noninvasive ventilation, mechanical ventilation or ECMO),
 - c. Evidence of shock (SBP < 90 mm Hg, DBP < 60 mm Hg, or requiring vasopressors),
 - d. Significant acute renal, hepatic, or neurologic dysfunction,
 - e. Admission to an ICU, or
 - f. Death.
- 3.7.1.2 Case Definition for Non-Severe COVID-19
 - Confirmed COVID-19 disease (per Section 3.7.1);
 - Does not meet the case definition of Severe COVID-19 disease (Section 3.7.1.1)

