6.1.2.7 COVID-19 Assessment Visit

For both the Phase 2 and Phase 3 segments of the study, subjects will be evaluated during a COVID-19 assessment visit when acute COVID-19 is suspected based on symptoms or positive SARS-CoV-2 testing. The assessment visit may be performed in the clinic, subject's vehicle, or at a home visit and should be performed within 3 days of a positive SARS-CoV-2 test or site knowledge of COVID-19 symptom onset. The virologic-confirmation of a case will be based on SARS-CoV-2 RT-PCR testing from the central lab. A local RT-PCR result will be considered acceptable in the case where a subject is hospitalized and a sample for central lab analysis is not able to be obtained, if it was obtained using. an assay performed by a laboratory accredited according to standards set by a national or regional accreditation body.

If a local lab is used to confirm the case, the report from the laboratory must be provided.

Phase 2 and Phase 3 segments: The following evaluations will be performed at this visit:

- Collect all present and/or new or ongoing AEs (Section 6.4.4); Only SAEs, AESIs and MAAEs will be reported after the Day 56 Visit;
- Document any present conditions and concomitant illnesses;
- Record current concomitant medications/treatments (Section 6.4.6);
- Optional targeted physical examination (Section 6.4);
- Record vital signs (Section 6.4);

Phase 2 only:

• Collect nasal swabs and saliva for SARS-CoV-2 RT-PCR detection (Section 6.4.8).

Phase 3 only:

- Collect whole blood and serum for cellular and humoral immunology assessment, where possible (Phase 3 cellular immunology collection at selected sites only)(Section 6.5)
- Collect nasopharyngeal swabs for SARS-CoV-2 RT-PCR testing (Section 6.4.8).

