8.5.1 PRIMARY ANALYSIS

Phase 2 Segment

Post-baseline increases from baseline in interferon-γ ELISpot response magnitudes will be compared between treatment groups using differences in medians and associated non-parametric 95% CIs.

INO-4800	COVID19-311
Inovio Pharmaceuticals, Ind	. Clinical Protocol

Post-baseline increases from baseline in neutralizing antibody response titers will be compared between treatment groups using ratios of geometric mean fold-rises and associated t-distribution based 95% CIs.

The summaries listed above will be stratified according to NP positive/negative status of the subjects. Valid samples for statistical analysis purposes will be those collected: at least 6 and no more than 30 days after Dose 2 for the Week 6 timepoint; at least 174 and no more than 198 days after Dose 2 for the Week 30 timepoint; and at least 356 and no more than 380 days after Dose 2 for the Week 56 timepoint. Baseline is defined as the last measurement prior to the first treatment administration.

The PP population will be used for these immunogenicity analyses.

Phase 3 Segment

Among subjects who are SARS-CoV-2 seronegative at baseline, the primary hypothesis of relative efficacy greater than 30% will be tested with H₀: $p \ge 0.70/(0.70+k)$ vs. H₁: p < 0.70/(0.70+k), where p is the true proportion of subjects with disease who receive INO-4800 relative to the total number of subjects with disease, and k is the total amount of follow-up time in the placebo group divided by the total amount of follow-up time in the INO-4800 group.

A p-value for this hypothesis test and corresponding confidence interval will be computed based on the exact binomial method of Clopper-Pearson. Success will be concluded if the one-sided p-value is <0.022 and the corresponding lower bound of the two-sided 95.6% Cl for efficacy exceeds 30% (alpha-level adjusted for interim analyses, see Section 8.5.6), and the point estimate for efficacy exceeds 50%.

For calculating k, an individual subject's follow-up time is either:

- $\circ~$ the date of first disease diagnosis date of the start of surveillance period +1 (for subjects who are cases), or
- the date of last follow-up date of the start of surveillance period +1 (for subjects who are non-cases).

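### A local RT-PCR counts only if the subject is hospitalized, so a locally confirmed subject who dies before admission fails the Phase 3 case and severe-case definitions

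*Protocol*

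**What the plan says.** All references are to Protocol version 5.0, Phase 3 segment.

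- **Main rule (section 3.7.1).** Disease is confirmed by "Positive testing by SARS-CoV-2 RT-PCR assay (performed at central lab*) with fever", or by the same central test with any one listed symptom.
- **Exception (footnote to 3.7.1).** "Local lab results will be accepted if the subject is hospitalized and a sample is not able to be obtained" for the central laboratory.
- **Exception repeated (section 6.1.2.7).** "A local RT-PCR result will be considered acceptable in the case where a subject is hospitalized" and no central sample can be had. This section adds that the local laboratory must be accredited and that its report must be supplied.
- **Route to a central swab outside hospital (6.1.2.7).** "The assessment visit may be performed in the clinic, subject's vehicle, or at a home visit", within 3 days of a positive test or of the site learning of symptoms.
- **Severe disease (3.7.1.1).** "Confirmed COVID-19 disease (per Section 3.7.1) with any of the following"; death is item f of the list that follows.
- **Death endpoint 2c (section 3.4).** "Incidence of deaths due to COVID-19", with no definition of its own. Section 8.2 describes this analysis as one of cases that end in death.
- **Follow-up time (8.5.1).** It runs to the last follow-up date "for subjects who are non-cases".
- **Missing data (8.5.8).** Nothing is imputed, but the supportive ITT efficacy analysis counts subjects with missing or unevaluable case status as cases.

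**The concern.** The exception rests on two joint conditions, and only one of them, that no central sample can be obtained, concerns the evidence. The quality of the local test is secured separately by the accreditation and report conditions in 6.1.2.7. Admission adds nothing to either. It does decide whether the same laboratory result counts: an admitted subject who cannot be swabbed is a case, while a subject with the same illness and the same local result who dies on the way to hospital is not.

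Two things are at stake. Some of the most serious outcomes can be missing from the severe and COVID-19-death counts, which will be small. And acceptance depends on hospitalization, which happens after randomization and which the vaccine may affect. If vaccinated cases are admitted less often, their local-only results are accepted less often, which favours the vaccine.

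**Working it through.** **1. The plan's own figures.** Inputs from Table 2 and sections 8.5.1, 8.5.6 and 8.6: 2238 placebo and 4476 vaccine seronegative subjects, attack rate 3.7%, true efficacy 60%, 149 cases, 90% power.

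- Expected placebo cases: 2238 × 0.037 = 82.8.
- Expected vaccine cases: 4476 × 0.037 × 0.40 = 66.2.
- Total: 149.05, against 149 stated.
- N = 149 / [(0.037 + 2 × 0.0148)/3] = 149 / 0.0222 = 6712, against 6714 stated.
- Power, with k = 0.5: p0 = 0.70/1.20 = 0.5833 and p1 = 0.40/0.90 = 0.4444. With looks at 75, 112 and 149 cases and one-sided alphas of 0.0016, 0.0092 and 0.022, exact power is 91.6%, against 90% stated.

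The design figures reproduce.

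**2. The definition applied to four symptomatic subjects, each with a positive accredited local RT-PCR.**

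| Subject | Central sample | Case under 3.7.1 | Severe case under 3.7.1.1 |
|---|---|---|---|
| Admitted, cannot be swabbed centrally | No | Yes, by the exception | Yes, if any listed item is met |
| At home, swabbed at a home or vehicle visit | Yes | Yes, if the central test is positive | Yes, if any listed item is met |
| Dies before admission | No | No | No, although death is item f |
| Not admitted, cannot be reached for a swab | No | No | No |

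**3. Does another rule recover the last two rows?**

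- Adjudication: section 7.11 has the EAC decide according to the case definition. The charter is not shown.
- Later PCR: Table 4 schedules RT-PCR only on Day 0 and at the assessment visit. The convalescent visit (6.1.2.8) takes serology and immunology samples only.
- Seroconversion: 3.7.2 requires no symptoms since the last negative serology, so a symptomatic seroconverter does not count as an asymptomatic infection.
- Primary per-protocol analysis: no imputation, so the subject stays a non-case. If the missed swab were ruled a protocol violation, the subject would leave the population instead (8.4). Either way the event is not counted.
- Supportive ITT analysis: such a subject is counted as a case where case status is treated as missing or unevaluable.
- Deaths: all-cause mortality (endpoint 1e) includes them, and 7.11 sends a serious unconfirmed event to SAE reporting.

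**4. Size for the primary endpoint (illustration).** The protocol gives no rate of local-only results or of admission. Assume that a share u = 1% to 10% of non-hospitalized cases have only a local result, and that a share h = 2% to 20% of cases are admitted. Counted cases in an arm = expected cases × [1 − u(1 − h)].

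- Smallest loss among the settings tried (u = 1%, h = 20% placebo, 2% vaccine): 82.8 × 0.01 × 0.80 + 66.2 × 0.01 × 0.98 = 1.3 cases.
- Largest loss (u = 10%, h = 5% in both arms): 149.05 × 0.10 × 0.95 = 14.2 cases.
- Efficacy with equal admission among cases: the factor cancels, leaving 60.0%.
- Efficacy in the most unequal setting (u = 10%, h = 20% placebo, 2% vaccine): 1 − 0.40 × (0.902/0.920) = 60.8%.

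The trial is case-driven, so uncounted cases lengthen accrual but do not lower the number on which power rests.

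**The case against.** The rule is deliberate and consistent. Sections 3.7.1 and 6.1.2.7 agree, and the version 5.0 summary of changes (item 13) states the intent: central testing for the primary endpoint, a hospital exception, and no self-collected samples. Trading a little sensitivity for a uniform assay is defensible, and missed cases that do not depend on arm leave a ratio estimate unbiased. The severe and death endpoints carry confidence intervals but no tests (8.5.2.1). All of this stands, and it argues against rewriting the primary definition.

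It also rules out several stronger readings that a reader might infer:

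- *Anyone who cannot be swabbed is lost.* Not so. A hospitalized subject who cannot be swabbed is the one the exception accepts, and home and vehicle visits (6.1.2.7, 6.4.8) cover most people isolating at home.
- *Such a subject is a non-case in every analysis.* Not so, given the ITT rule in 8.5.8.
- *The death is certainly not a COVID-19 death.* Endpoint 2c does not cite 3.7.1. Sections 3.7.1.1 and 8.2 point that way, but the endpoint is undefined and the EAC charter is not shown.
- *Several deaths and many cases will be lost.* Applying the 2.3% case-fatality ratio in section 1.2 to 149 cases gives 3.4 deaths, but the same section says such ratios are probably too high. Taking 5% to 10% of 149 as local-only gives 7 to 15 cases, but that share is assumed and makes no allowance for home visits. Neither figure is an estimate.

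What the objection does not answer is the subject who dies before admission. No home visit, later PCR or serology rule applies, and central testing gains nothing there, because no central sample will ever exist.

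**Conclusion.** The point holds in a narrow form. Hospitalization is a necessary condition for any local RT-PCR to count. A symptomatic, locally positive subject who dies before admission, or the uncommon non-hospitalized subject who cannot be reached for a swab, therefore fails the case definition. That subject does not count as a case in the primary per-protocol analysis and cannot be a severe case through death. For endpoint 2c the same follows by implication from section 8.2, not from a stated definition.

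This is a gap in how the rule is fixed, not a contradiction between sections. The effect on the primary result is negligible: efficacy stays at 60.0%, or reaches at most about 60.8% under the assumed ranges above. The importance lies in the severe and COVID-19-death endpoints, where counts are sparse and inclusion depends on a post-randomization event. The protocol gives no basis for estimating how many events would be lost there. It is a cheap improvement, not a flaw that threatens the trial's conclusion.

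**What to change.** 1. In the footnote to 3.7.1 and in 6.1.2.7, extend the existing exception to subjects who died before a central sample could be obtained. Keep the accreditation and laboratory-report conditions of 6.1.2.7, and exclude self-collected specimens. Align the EAC charter.
2. Keep central confirmation in all other situations. Accepting a local result whenever a central swab was missed would reverse the deliberate central-laboratory choice and make acceptance depend on site effort.
3. Pre-specify a sensitivity analysis of the primary, severe and COVID-19-death endpoints that counts every accredited local positive in a subject who otherwise meets the definition, regardless of hospitalization. This covers the subject who could not be reached.

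The cost is a change of wording in two sections and the charter, plus one added analysis. The downside is that a very few cases will rest on a local assay. The change should be made before unblinding, since it would not be credible afterwards.
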